11.1.3. Statistical Methodology Specification

Endpoint / Variables

 Log₁₀ maximum change from baseline to day 8 in plasma RNA, Log₁₀ change from baseline to Day 8 in plasma HIV-1 RNA relative to the PK parameters (AUC(0-τ), C_{max} and C_{τ}) Day 8/9/10 from Part 1 and Day 7 from Part 2
Model Specification

 To model the exposure-response relationship, a frequentist three-parameter E_{max} model is planned. This model assumes the following form $\Delta VL = E0 + \frac{Emax}{1 + \left(\frac{EC50}{PK}\right)} + \epsilon$ 
Where:
 
 ΔVL is the log₁₀ maximum viral load change from baseline to day 8 or change to Day 8 in plasma HIV-1 RNA E0 is the baseline response Emax is the maximum response

CONFIDENTIAL

208132

- EC50 is the corresponding exposure/PK parameter value that attains the 50% of the maximal effect
- PK is the PK parameter
- ϵ is a random error assumed to be normally distributed with mean zero and constant variance (σ^2)
- If problems are encountered Emax model or if the Emax shape is a poor fit for the data and a linear relationship looks plausible across the dose range, then a linear model will be considered of the form:

$$\Delta VL = \alpha * PK + \epsilon$$

Model Checking & Diagnostics

- Model assumptions will be applied, but appropriate adjustments may be made based on the data.

Model Results Presentation

- The derived data from this Emax model (estimates E0, Emax, EC50 and Variance along with their standard error, and 95% CI) will be tabulated and an exposure-response curve will also be produced. If E0 turns out as not significant, the reduced Emax model without baseline E0 will be selected as the final model.

Example SAS Code:

```
PROC NLMIXED;
PARMS E0 = EST EMAX = EST EC50 = EST S2E = SE;
BOUNDS E0>0 EMAX>0 EC50>0 S2E>0;
PRED = E0 +(EMAX-E0)/(1+(EC50/PARAM));
MODEL RESPONSE ~ NORMAL (PRED, S2E);
PREDICT PRED OUT=DOSE;
RUN;
```

11.2. Concentration-QTcF Analyses

For each ECG assessment, the individual subject's QTcF change from baseline will be calculated and will be merged with time-matched PK concentration values, when available. QTcF change from baseline (y-axis) to Day 8 for all doses in Part 1 and Part 2 will be plotted against the PK concentration data (x-axis) with a linear regression overlay. The placebo arms from Part 1 and Part 2 would be combined as one group (with PK concentration value as 0) and included in the figure.

CONFIDENTIAL

208132

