2.2. Part 1 and Part 2 Treatment, Post-Dosing and Follow-up Periods

Study Part 1:

Procedure ¹	Treatment Period Day 1 – Day 10									Post-Dosing Follow Up Period Day 11 – 17			Final Follow-up Day 18-24	
	Day 1	Day 2	Day 3, 4 Choose one day for the Clinic Visit 3. The other day will be a virtual event.		Day 5, 6, 7 Choose one day for the Clinic Visit 4. The other days will be virtual events.			Day 8, 9, 10 Choose one day for the Clinic Visit 5. The other days will be virtual events.			Day 11	Day 12	Day 13, 14, 15, 16 or 17	Day 18, 19, 20, 21, 22, 23 or 24
	Clinic Visit 1	Clinic Visit 2	Clinic Visit 3	Virtual	Clinic Visit 4	Virtual	Virtual	Clinic Visit 5	Virtual	Virtual	Clinic Visit 6	Clinic Visit 7	Clinic Visit 8	Clinic Visit 9
Clinical Assessments														
Outpatient Visit ²	X	X	X		X			X			X	X	X	X
Video/Phone Call				X		X	X		X	X				
Verify Inclusion/Exclusion Criteria	X													
Medical/medication/drug/alcohol history	X													
Prior Anti-retroviral (ARV) Check	X													
CDC Classification	X													X

Procedure ¹	Treatment Period Day 1 – Day 10										Post-Dosing Follow Up Period Day 11 – 17			Final Follow-up Day 18-24
	Day 1	Day 2	Day 3, 4 Choose one day for the Clinic Visit 3. The other day will be a virtual event.		Day 5, 6, 7 Choose one day for the Clinic Visit 4. The other days will be virtual events.			Day 8, 9, 10 Choose one day for the Clinic Visit 5. The other days will be virtual events.			Day 11	Day 12	Day 13, 14, 15, 16 or 17	Day 18, 19, 20, 21, 22, 23 or 24
	Clinic Visit 1	Clinic Visit 2	Clinic Visit 3	Virtual	Clinic Visit 4	Virtual	Virtual	Clinic Visit 5	Virtual	Virtual	Clinic Visit 6	Clinic Visit 7	Clinic Visit 8	Clinic Visit 9
HIV-associated conditions assessments ³	X	X	X	X	X	X	X	X	X	X	X	X	X	X
Adverse event (AE)/SAE assessment ³	X	X	X	X	X	X	X	X	X	X	X	X	X	X
Concomitant medication review ³	X	X	X	X	X	X	X	X	X	X	X	X	X	X
Weight, BMI and Physical exam ⁴	X													
Vital Signs	X	X	X					X						X
C-SSRS Administration (Since Last Visit form)											X			

Procedure ¹	Treatment Period Day 1 – Day 10									Post-Dosing Follow Up Period Day 11 – 17			Final Follow-up Day 18-24	

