	Day 1	Day 2	Day 3, 4 Choose one day for the Clinic Visit 3. The other day will be a virtual event.		Day 5, 6, 7 Choose one day for the Clinic Visit 4. The other days will be virtual events.			Day 8, 9, 10 Choose one day for the Clinic Visit 5. The other days will be virtual events.			Day 11	Day 12	Day 13, 14, 15, 16 or 17	Day 18, 19, 20, 21, 22, 23 or 24
	Clinic Visit 1	Clinic Visit 2	Clinic Visit 3	Virtual	Clinic Visit 4	Virtual	Virtual	Clinic Visit 5	Virtual	Virtual	Clinic Visit 6	Clinic Visit 7	Clinic Visit 8	Clinic Visit 9
Clinical Procedures														
12-lead ECG (triplicate reading, pre-dose; single readings at PK draws 2hr, 4hr, and 6hr)	X													
12-lead ECG (single reading, pre-dose at Visits 2 and 3)		X	X											X
12-lead ECG (single reading pre-dose and at PK draws 2hr, 4hr, and 6hr)								X						
Pharmacogenetics (PGX) Collection (if consented)	X													

Procedure ¹	Treatment Period Day 1 – Day 10									Post-Dosing Follow Up Period Day 11 – 17			Final Follow-up Day 18-24	
	Day 1	Day 2	Day 3, 4 Choose one day for the Clinic Visit 3. The other day will be a virtual event.		Day 5, 6, 7 Choose one day for the Clinic Visit 4. The other days will be virtual events.			Day 8, 9, 10 Choose one day for the Clinic Visit 5. The other days will be virtual events.			Day 11	Day 12	Day 13, 14, 15, 16 or 17	Day 18, 19, 20, 21, 22, 23 or 24
	Clinic Visit 1	Clinic Visit 2	Clinic Visit 3	Virtual	Clinic Visit 4	Virtual	Virtual	Clinic Visit 5	Virtual	Virtual	Clinic Visit 6	Clinic Visit 7	Clinic Visit 8	Clinic Visit 9
Hematology/Chem istry/Urine	X	X	X		X			X			X			X
Fasting Lipid Panel (approximately 8 hrs)	X										X			X
Lymphocyte T-cell subsets (CD4, CD8)	X										X			
Plasma for HIV-1 genotype/phenoty pe ⁵	X	X	X		X			X			X	X	X	X
Plasma for storage ⁶	X	X	X		X			X			X	X	X	X
HIV-1 RNA	X	X	X		X			X			X	X	X	X

Procedure ¹	Treatment Period Day 1 – Day 10									Post-Dosing Follow Up Period Day 11 – 17			Final Follow-up Day 18-24	
	Day 1	Day 2	Day 3, 4 Choose one day for the Clinic Visit 3. The other day will be a virtual event.		Day 5, 6, 7 Choose one day for the Clinic Visit 4. The other days will be virtual events.			Day 8, 9, 10 Choose one day for the Clinic Visit 5. The other days will be virtual events.			Day 11	Day 12	Day 13, 14, 15, 16 or 17	Day 18, 19, 20, 21, 22, 23 or 24

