	Clinic Visit 1	Clinic Visit 2	Clinic Visit 3	Virtual	Clinic Visit 4	Virtual	Virtual	Clinic Visit 5	Virtual	Virtual	Clinic Visit 6	Clinic Visit 7	Clinic Visit 8	Clinic Visit 9
Single, Pharmacokinetic (PK) sample (pre- dose at Visits 3 and 4)			X		X						X ⁷	X	X	
Intensive PK sampling ⁸ (with sample at 24hr time point the next morning)	X							X ⁹						
Observed dosing with GSK3640254/plac ebo ³	X	X	X	X	X	X	X	X	X	X				
IWRS (RAMOS) activity ¹⁰	X													

1. Procedures should be performed in the following order: ECG, Vitals, Blood Draws, followed by dose administration.
 2. The study requires 9 in-clinic visits. Flexibility is offered for Visits 3, 4, 5, 8 and 9. The visit schedule for each participant should be pre-planned to be sure weekend, work schedules and clinic hours are appropriately considered. No visit interval during the treatment period can be greater than 3 days.
 3. These assessments must be conducted with a participant during each day indicated, to include the days when the participant is not in the clinic. This can be done in via phone, preferably via a visual method (as locally permitted) of Skype, Facetime, WhatsApp, et. al.
 4. Physical Exam will include, at a minimum, assessments of the Skin, Heart, Lungs, and Abdomen (liver and spleen).
 5. Genotypic/Phenotypic testing will be conducted on Day 1 and Day 11 samples, with other visits tested as appropriate.
 6. Plasma samples for storage will be collected at each visit starting at Day 1, including unscheduled visits. These samples will be used when needed, such as when samples are lost or where quantity is insufficient for testing. In the event samples are not used by study completion, they will be utilized for additional research on ARV resistance and/or HIV-1 disease biology/host immune response (excluding any human genetic testing)
 7. If the Intensive PK day occurs on Day 10, do not collect the Day 11 pre-dose PK sample (as it is redundant with the 24-hr PK collection (completing the sample set started on Day 10).
 8. Intensive Plasma PK samples will be collected as outlined in [Table 4](#) in Section 9.5
 9. If Day 8 or 9 is the Clinic Visit 5 to include the Intensive PK collection, the participant must return the following day for the 24-hr PK collection, meal and dosing. The assessments to be done as indicated on what is a “virtual visit day” should be captured as a virtual visit, even if the questions are asked in the clinic.

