Procedure ¹	Treatment Period Day 1 – Day 7						Post-Dosing Follow Up Period	Final Follow- up	
	Day 1	Day 2	Day 3, 4 Choose one day for the Clinic Visit 3. The other day will be a virtual event.		Day 5, 6 Choose one day for the Clinic Visit 4. The other day will be a virtual event.		Day 7	Day 8	Day 10, 11 or 12
	Clinic Visit 1	Clinic Visit 2	Clinic Visit 3	Virtual	Clinic Visit 4	Virtual	Clinic Visit 5	Clinic Visit 6	Clinic Visit 7
Clinical Procedures									
12-lead ECG (triplicate reading, done pre-dose; single readings at PK draws 2hr, 4hr, and 6hr)	X								
12-lead ECG (single reading, done pre-dose at Visits 2 and 3)		X	X						X
12-lead ECG (single reading done pre-dose and at PK draws 2hr, 4hr, and 6hr)							X		

Procedure ¹	Treatment Period Day 1 – Day 7						Post-Dosing Follow Up Period	Final Follow- up	
	Day 1	Day 2	Day 3, 4 Choose one day for the Clinic Visit 3. The other day will be a virtual event.		Day 5, 6 Choose one day for the Clinic Visit 4. The other day will be a virtual event.		Day 7	Day 8	Day 10, 11 or 12
	Clinic Visit 1	Clinic Visit 2	Clinic Visit 3	Virtual	Clinic Visit 4	Virtual	Clinic Visit 5	Clinic Visit 6	Clinic Visit 7
Pharmacogenetics (PGX) Collection (if consented)	X								
Hematology/Chem istry/Urine	X	X	X		X		X	X	X
Fasting Lipid Panel (approximately 8 hrs)	X							X	X
Lymphocyte T-cell subsets (CD4, CD8)	X							X	
Plasma for HIV-1 genotype/phenoty pe ⁵	X	X	X		X		X	X	
Plasma for storage ⁶	X	X	X		X		X	X	X

Procedure ¹	Treatment Period Day 1 – Day 7						Post-Dosing Follow Up Period	Final Follow- up	
	Day 1	Day 2	Day 3, 4 Choose one day for the Clinic Visit 3. The other day will be a virtual event.		Day 5, 6 Choose one day for the Clinic Visit 4. The other day will be a virtual event.		Day 7	Day 8	Day 10, 11 or 12
	Clinic Visit 1	Clinic Visit 2	Clinic Visit 3	Virtual	Clinic Visit 4	Virtual	Clinic Visit 5	Clinic Visit 6	Clinic Visit 7
HIV-1 RNA	X	X	X		X		X	X	X
Single, Pharmacokinetic (PK) sample done pre-dose			X		X				
Intensive PK sampling (to include the 24hr samples drawn the next day)	X						X		
Observed dosing with GSK3640254 /placebo ³	X	X	X	X	X	X	X		

Procedure ¹	Treatment Period Day 1 – Day 7						Post-Dosing Follow Up Period	Final Follow- up	
	Day 1	Day 2	Day 3, 4 Choose one day for the Clinic Visit 3. The other day will be a virtual event.		Day 5, 6 Choose one day for the Clinic Visit 4. The other day will be a virtual event.		Day 7	Day 8	Day 10, 11 or 12

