11.1.2. Population of Interest

The primary pharmacodynamics analyses will be based on the PK/PD population, unless otherwise specified. Part 1 Day 9~11 HIV RNA are excluded to fulfil the same dosing days and be used in one statistical model.

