13.11.14. Pharmacokinetic / Pharmacodynamic Figures

Pharmacokinetic / Pharmacodynamic: Figures					
No.	Population	IDSL / TST ID / Example Shell	Title	Programming Notes	Deliverable [Priority]
PK/PD – RNA Change from Baseline					
6.1.	PK/PD	PK28	Scatter Plot of Day 8 HIV RNA Change from Baseline versus Plasma PK Parameters	Present Day 8 HIV RNA Change from Baseline vs AUC(0- τ), C _{max} and C _{τ} , for all doses in Part 1 and Part 2	SAC
6.2.	PK/PD	PK28	Scatter Plot of HIV RNA Maximum Change from Baseline to day 8 versus Plasma PK Parameters	Maximum change from baseline to day 8 HIV RNA vs AUC(0- τ), C _{max} and C _{τ} , for all doses in Part 1 and Part 2	SAC
PK/PD – QTcF Change from Baseline					
6.3.	PK/PD	PK28	Scatter Plot of QTcF Change from Baseline versus Time-matched PK Concentration	Placebo group included with PK concentration value as 0. Day 1 to Day 8 in Part 1 and Part 2.	SAC

CONFIDENTIAL

208132

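### Taken literally, the Day 8 limit on the concentration-QTcF plot drops Part 1 Visit 5 for anyone seen on Day 9 or 10, including on 200 mg

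*SAP*

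**What the plan says.** SAP 11.2 merges each participant's QTcF change from baseline with the time-matched PK concentration, where there is one. It then specifies the figure: "QTcF change from baseline (y-axis) to Day 8 for all doses in Part 1 and Part 2 will be plotted", with a linear regression overlay and the two placebo arms pooled at concentration zero. The Figure 6.3 entry in SAP 13.11.14 gives the same limit: "Placebo group included with PK concentration value as 0. Day 1 to Day 8 in Part 1 and Part 2".

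The Part 1 schedule (Protocol 2.2) lets the site place Visit 5: "Day 8, 9, 10 Choose one day for the Clinic Visit 5". That visit carries "12-lead ECG (single reading pre-dose and at PK draws 2hr, 4hr, and 6hr"), taken with the second intensive PK profile. In Part 2 the corresponding visit is fixed on Day 7, with "12-lead ECG (single reading done pre-dose and at PK draws 2hr, 4hr, and 6hr"), and no ECG is scheduled on Day 8.

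Two neighbouring SAP sections bear on how to read the limit. SAP 11.1.2 says "Part 1 Day 9~11 HIV RNA are excluded to fulfil the same dosing days and be used in one statistical model". SAP 11.1.3 defines the repeat-dose PK parameters as coming from "Day 8/9/10 from Part 1 and Day 7 from Part 2".

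**The concern.** A programmer who applies study day 8 or earlier will discard the whole of Visit 5 for every Part 1 participant whose visit fell on Day 9 or 10. Those are repeat-dose points near peak concentration. At 200 mg they are also the highest concentrations the study is expected to produce, and 200 mg is not given in Part 2. High-concentration points have the most leverage on a regression line, so the figure would be thinned where it is most informative. Figure 6.3 is the only concentration-QTc display planned.

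The stated reason for leaving out Part 1 Days 9 to 11 is to equalise dosing days for HIV RNA, a response that builds up over days of treatment. It does not carry over to this figure, where each ECG is paired with the concentration measured at the same time.

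**Working it through.** **ECG/PK pairs per Part 1 participant** (Protocol 2.2, Part 1 schedule, and Protocol Table 4). The Day 1 pre-dose triplicate is the baseline and is not counted.

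| Occasion | ECG | Matching PK | Pairs |
|---|---|---|---|
| Day 1 | 2, 4, 6 h | intensive profile | 3 |
| Day 2 | pre-dose | 24 h sample of the Day 1 profile | 1 |
| Visit 3 | pre-dose | single pre-dose sample | 1 |
| Visit 5 | pre-dose, 2, 4, 6 h | intensive profile | 4 |

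Total: 3 + 1 + 1 + 4 = 9. The 2, 4 and 6 h readings bracket the repeat-dose Tmax of 3.8 to 4.3 h reported in Protocol 3.2.2.

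**Applying the Day 8 limit literally**
- Part 1, Visit 5 on Day 8: 9 of 9 kept.
- Part 1, Visit 5 on Day 9 or 10: 9 − 4 = 5 kept, and 0 of the 3 repeat-dose post-dose pairs.
- Part 2, Visit 5 on Day 7: 9 of 9 kept.

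**What else the limit removes.** For active participants, nothing. The Part 1 Visit 9 ECG has no PK sample: the row headed "Single, Pharmacokinetic (PK) sample (pre- dose at Visits 3 and 4") continues to Visits 6, 7 and 8 only. The Part 2 Visit 7 ECG has none either. The time-matching rule already leaves both out.

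**200 mg arm, planned n = 6.** There are 6 × 9 = 54 pairs, of which 6 × 3 = 18 are repeat-dose post-dose. With k late participants, 54 − 4k and 18 − 3k remain:

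| k | Pairs kept of 54 | Repeat-dose post-dose kept of 18 |
|---|---|---|
| 0 | 54 | 18 |
| 1 | 50 | 15 |
| 3 | 42 | 9 |
| 6 | 30 | 0 |

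These are upper bounds, because Figure 6.3 uses the PK/PD population, which requires Per-Protocol status (SAP 4). Over all 12 planned Part 1 active participants the loss is 0 to 48 of 108 pairs (0 to 44%). Over both parts it is 0 to 48 of 270 active pairs (0 to 18%).

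**Concentration range lost (assumption: patients behave like the healthy participants).** Protocol Table 2 predicts a mean steady-state Cmax of 1629 ng/mL at 200 mg. Protocol 3.2.2 gives a Day 14 to Day 1 Cmax ratio of 1.9 to 2.3. Day 1 Cmax would then be 1629/2.3 = 708 to 1629/1.9 = 857 ng/mL, and a late 200 mg participant's remaining post-dose points would all lie at that level. For comparison, log-log interpolation of Table 2 between 100 mg (879) and 200 mg (1629) puts 140 mg, the top Part 2 dose in SAP 2.3, at about 1186 ng/mL. Those points stay in the figure.

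**Scale in milliseconds (illustration only).** The two predictions in Protocol 3.2.2 (5.38 ms at 1779 ng/mL, 6.70 ms at 2154 ng/mL) define a line with slope (6.70 − 5.38)/(2154 − 1779) = 0.00352 ms per ng/mL and intercept 5.38 − 0.00352 × 1779 = −0.88 ms. It gives 1.6 ms at 708, 2.1 ms at 857, 3.3 ms at 1186 and 4.9 ms at 1629 ng/mL. These are placebo-corrected values from another study; Figure 6.3 plots uncorrected change from baseline.

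**Effect on the slope (rough).** Assumptions: Table 2 mean concentrations, accumulation 1.9 to 2.3, nine pairs per person, independent errors, placebo at zero, and the same number late in the 10 mg and 200 mg arms. The standard error of the slope then rises by 4 to 5% with 1 late per arm, about 15% with 3 and 41 to 46% with all 6.

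**The case against.** The strongest reply is that Day 8 is shorthand for Visit 5. SAP 13.3.1 presents analyses by scheduled visit, and its Part 1 ECG window maps Days 8 to 10 to Visit 5. The Table 4.11 note also labels the repeat-dose PK day as Day 8 for both parts. On that reading no pair is lost. This stands as a plausible reading, but it does not settle the matter. SAP 11.1.3 spells out the range of days when it means Visit 5, and SAP 11.1.2 treats Day 8 as a calendar limit.

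A second reply is that the limit deliberately harmonises a 10-day and a 7-day part. The sentence giving that reason names HIV RNA only, and pairs matched in time do not need equal dosing days.

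Other points on size do stand:
- No treatment-period visit interval may exceed 3 days. Of the 9 permitted day combinations for Visits 3, 4 and 5, 5 put Visit 5 on Day 8, 3 on Day 9 and 1 on Day 10. These are not probabilities, but all six late is an extreme.
- Late placebo participants lose no concentration information, since theirs is set to zero.
- The output is exploratory, with no planned slope interval, threshold or decision rule, and SAP 2.4 states that no formal hypotheses are tested.
- QTc stopping criteria, by-visit ECG tables, maximum-QTc summaries and QTc-time plots keep every Visit 5 ECG. The concentration-QTc model from Study 207187 is also independent of this figure.

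**Conclusion.** The concern holds as a defect in the written rule. Followed literally, it discards 4 of 9 valid pairs per late Part 1 participant, including all 3 repeat-dose post-dose pairs, with no stated reason that applies to ECG data.

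The realised size is unknown. Protocol 3.2.4 describes genotyped Visit 5 samples as from Day 8 or 9, which suggests that some visits fell on Day 9, but it gives no counts. The loss therefore lies between nothing and all 18 repeat-dose post-dose pairs at 200 mg. The pair counts follow directly from the schedule. The concentration, millisecond and standard-error figures rest on healthy-volunteer data and simplifying assumptions, and serve only for scale. No participant protection or main conclusion depends on this plot. The correction is still worth making, because it costs almost nothing and is right on either reading.

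**What to change.** In SAP 11.2 and in the Figure 6.3 programming note, replace the Day 8 limit with: all on-treatment time-matched ECG/PK pairs through Visit 5 (Day 8, 9 or 10 in Part 1; Day 7 in Part 2). Restricting to on-treatment pairs also keeps follow-up placebo ECGs, which would otherwise qualify at concentration zero, out of the figure. Every participant with complete data then contributes 9 of 9 pairs.

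The cost is two wording edits, with no new data, output or analysis. If Visit 5 was meant all along, the figure does not change. If a calendar limit at Day 8 was intended for QTcF, the SAP should say so and give a reason that applies to ECG data.

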In the SAD, seventeen subjects experienced 60 individual AEs (58 Grade 1; 2 Grade 2). The 2 Grade 2 AEs were headache and depression (both unrelated). The most frequent AEs were Headache (6 subjects), Contact Dermatitis primarily due to electrocardiogram (ECG) electrodes (5 subjects), and Diarrhea (4 subjects). There was no dose/AE relationship.

In the MAD, 43 subjects experienced 126 individual AEs (123 Grade 1; 3 Grade 2). The 3 Grade 2 AEs were headache (one related and one unrelated) and back pain (unrelated). The most frequent AEs were Headache (15 subjects), Contact Dermatitis (8 subjects), Dizziness (7 subjects), Contusion (6 subjects), Fatigue (6 subjects), and Back Pain (4 subjects).

There were no clinically significant abnormal fluctuations or trends in vital signs in the SAD or MAD cohorts. There were no abnormal clinically significant arrhythmias or QT prolongations (values >500 ms or increases >60 ms from Baseline) observed for any participant in the SAD or MAD. A cardiodynamic evaluation of healthy subjects in the MAD portion of Study 207187 (placebo or GSK3640254 dose range 50 to 320 mg daily for 14 days) was performed. Serial ECGs were extracted from continuous Holter monitors at time-matched baseline on Day -1 and for approximately 24 hours post-dose on Days 1 and 14. In the concentration-QTc analysis, a final model with a treatment effect-specific intercept reasonably represented the data. The slope of the concentration-QTc relationship was 0.004 ms per ng/mL (90% confidence interval [CI]: 0.0023 to 0.0048) with a small treatment effect-specific intercept of -0.9 ms (90% CI: -4.47 to 2.69). The QT effect ($\Delta\Delta\text{QTcF}$) of GSK3640254 could be predicted to be 5.38 ms (90% CI: 1.66 to 9.10) and 6.70 ms (90% CI: 2.79 to 10.61) for the 200 mg (1779 ng/mL) and 320 mg (2154 ng/mL) doses, respectively, on Day 14. Based on this concentration-QTc analysis, a QTcF effect above 10 ms could be excluded up to GSK3640254 plasma concentrations of approximately 2000 ng/mL (corresponding to doses approximately \leq 200 mg QD; note, the maximum dose used in Part 1 of this study, 208132, is 200 mg QD). Finally, there were no laboratory abnormality trends across doses that were clinically significant or associated with any symptoms.

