Table 4 Intensive Pharmacokinetic Sampling Schedule and Other Activities at Clinic Visit 1 and Clinic Visit 5

	Time (Event)	Window for blood draw	Time (Relative to Dosing) Hour: Min
Clinic Visit 1 And Clinic Visit 5	morning pre-dose work: ECGs, vitals and full blood draw to include the pre-dose PK collection		
	Eat Meal. Administer study treatment and start the clock for subsequent blood draws.		00:00
	1 hr PK blood draw	± 5 minutes	01:00
	2 hr ECG and PK blood draw	± 15 minutes	02:00
	3 hr PK blood draw	± 15 minutes	03:00
	4 hr ECG and PK blood draw	± 15 minutes	04:00
	5 hr PK blood draw	± 15 minutes	05:00
	6 hr ECG and PK blood draw	± 15 minutes	06:00
	8 hr PK blood draw	± 30 minutes	08:00
	12 hr PK blood draw	± 2 hours	12:00
Next Day	24 hr (morning pre-dose) PK blood draw ^{1,2}	± 2 hours	24:00
	Eat Meal and administer study treatment.		

1. This 24-hr pre-dose PK blood draw will be done at the same time as the collection for the lab kit on the next day.

2. In study Part 1, if the Visit 5 Intensive PK visit is done on Day 10, this 24-hr PK blood draw will be done at the same time as the collection for the lab kit on Day 11. Otherwise, this 24-hr blood draw is the only draw done on Day 9 (if the clinic visit is done on Day 8) or Day 10 (if the clinic visit is done on Day 9).

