2.3. Study Design

Overview of Study Design and Key Features	

The diagram illustrates the study design, divided into Part 1 and Part 2. Part 1 starts with N=14 participants randomized on Day 1. They are assigned to three groups: GSK3640254 200 mg once daily (N=6), GSK3640254 10 mg once daily (N=6), and PLACEBO (N=2). Part 2 starts with N=20 participants randomized on Day 1. They are assigned to four groups: GSK3640254 Dose 90% Max Effect 140 mg (N=6), GSK3640254 Dose 75% Max Effect 80 mg (N=6), GSK3640254 Dose 30% Max Effect 40 mg (N=6), and PLACEBO (N=2). An unblinded interim analysis is conducted by the Study Team to confirm GO to Part 2 and refine Part 2 doses as needed. The timeline shows Day 1 Randomization, Follow-up at Day 10 for Part 1, and Day 1 Randomization, Follow-up at Day 7 for Part 2.
	
Design Features	
 This is a Phase 2a, global, multicentre, randomized, double-blind (Sponsor-unblinded), placebo-controlled, adaptive clinical trial to evaluate the antiviral effect, safety, tolerability and PK/ pharmacodynamics (PD) of GSK3640254 over 10 days in study Part 1 and over 7 days in study Part 2 in ART naïve HIV-1 infected adults, who are termed “participants” in the study. All participants will be screened for eligibility before being randomized, preferably within 14 days, into a 10-day treatment period in Part 1 and into a 7-day treatment in Part 2. The 14-day screening period may be extended to 28 days in some cases to allow receipt of all screening results and/or to accommodate scheduling.
Dosing	
 Part 1 will include approximately 14 randomized participants and will evaluate two active doses of GSK3640254, 200 mg once daily or 10 mg once daily, in cohorts of 6 participants each for 10 days. A cohort of 2 participants will be randomized to receive placebo for 10 days. Part 2 will include approximately 20 randomized participants and will evaluate three active doses of GSK3640254, 140/80/40 mg once daily, in cohorts of 6 participants each for 7 days. A cohort of 2 participants will be randomized to receive placebo for 7 days.
Time & Events	
 See Appendix 2: Schedule of Activities for additional details of activities
Treatment Assignment	
 All participants will be centrally randomized using an Interactive Voice/Web Response System (IVRS/IWRS).

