2.4. Statistical Hypotheses / Statistical Analyses

Study 208132 is a proof of concept (POC), randomized double blind (Sponsor-unblinded) study to characterize antiviral activity, safety/tolerability, PK, and the relationship between PK and antiviral activity of GSK3640254 given once daily (QD), administered across a range of doses over 10 days in Part 1 and over 7 days in Part 2 in HIV-1 infected treatment naïve adults. No formal hypotheses will be tested.

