8. SAFETY ANALYSES

The safety analyses will be based on the Safety population, unless otherwise specified. Safety data will be presented in tabular format and summarized descriptively according to GSK's Integrated Data Standards Library standards and data will be in Clinical Data Interchange Standards Consortium (CDISC) format. No formal statistical analysis of the safety data will be conducted.

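### The concentration-QTcF line in SAP 11.2 has no nominal-time term and no subject effect, so any post-meal or clock-time QTcF shift enters the line, and any interval taken from it would be too narrow

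*SAP*

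**What the plan says.** SAP 11.2 takes each participant's QTcF change from baseline, which "will be merged with time-matched PK concentration values, when available". The pairs up to Day 8, from all doses in both parts, "will be plotted against the PK concentration data (x-axis) with a linear regression overlay". Placebo participants from both parts are pooled at concentration zero. Figure 6.3 in SAP Appendix 11 repeats this and adds no model term, confidence band or slope table.

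Baseline is the Day 1 pre-dose value (SAP 5.2), averaged over three tracings (Protocol 8.1.2). Protocol Table 4 puts the pre-dose ECG first, then "Eat Meal. Administer study treatment and start the clock for subsequent blood draws", then ECGs at 2, 4 and 6 h.

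The earlier healthy-volunteer analysis in Protocol 3.2.2 was built differently: "Serial ECGs were extracted from continuous Holter monitors at time-matched baseline on Day -1". It also used a treatment-specific intercept and 90% intervals.

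**The concern.** The figure is meant to show how QTcF moves with concentration. Within an active arm, the highest concentrations on a given day are also the post-meal, later-in-the-day readings. The lower ones are morning pre-dose readings. A line on concentration alone cannot separate drug from meal and clock time. In SAP 11.2 the time-matching is between ECG and PK sample; the baseline is not matched by time of day. A post-meal fall in QTcF would hide part of a drug effect, and a rise would imitate one.

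Each participant also supplies up to nine pairs that share one baseline. Treating them as independent overstates the precision of any interval drawn from the line.

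QTc prolongation is among the major risks in Protocol 3.3, and Figure 6.3 is the only planned exposure-QTc display in this population.

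**Working it through.** **Plan's own figures.** SAP 11.2 states no slope, SE or sample size to reproduce. The QTc predictions in Protocol 3.2.2 can be checked against each other:

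- slope = (6.70 − 5.38) / (2154 − 1779) = 1.32 / 375 = 0.00352 ms per ng/mL
- intercept = 5.38 − 0.00352 × 1779 = −0.88 ms

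These agree with the printed 0.004 and −0.9 after rounding.

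**Inputs from the documents.**

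- Participants: 34, with 6 each at 10, 40, 80, 140 and 200 mg and 4 on placebo (SAP 2.3).
- ECG/PK pairs per participant: Day 1 at 2, 4 and 6 h; pre-dose at Visits 2 and 3; Visit 5 at pre-dose, 2, 4 and 6 h. That is 9 each, or 34 × 9 = 306.
- Part 1 Visit 5 may fall on Day 8, 9 or 10, while the plot stops at Day 8. If all Part 1 Visit 5 pairs are lost, 306 − 14 × 4 = 250 remain.
- tmax is about 4 h and half-life 22 to 29 h (Protocol 3.2.2); 25 h was used.
- Steady-state Cmax is 113, 389, 879 and 1629 ng/mL at 10, 40, 100 and 200 mg (Protocol Table 2). Interpolation gives 721 at 80 mg and 1186 at 140 mg.

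**Assumptions, because the documents are silent.** Total SD of QTcF change 8 ms; within-subject correlation 0 to 0.7; between-subject PK CV 30%. The shift is 0, or 5 ms at 2 and 4 h falling to 3 ms at 6 h, or 8 ms falling to 5 ms.

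One pointer on correlation: if readings are otherwise independent with equal variance, sharing a three-tracing baseline alone gives (1/3) / (1 + 1/3) = 0.25.

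**Bias of the plain line** (no drug effect, 3000 trials per scenario, predicted effect at 1629 ng/mL):

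| Assumed shift | All Visit 5 pairs kept | Part 1 Visit 5 dropped |
|---|---|---|
| 5 ms fall | about −1.4 ms | about −2.0 ms |
| 8 ms fall | about −2.3 ms | about −3.3 ms |
| 5 ms rise | about +1.5 ms | about +2.0 ms |

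This bias hardly changes with the assumed correlation. Across other concentration models, including one scaled to 1779 ng/mL at 200 mg, a 5 ms shift gives about 1.4 to 2.1 ms with all pairs kept and about 2.0 to 2.7 ms with Part 1 Visit 5 dropped. Against the protocol's 5.38 ms prediction for 200 mg, 1.4 / 5.38 = 26% and 2.1 / 5.38 = 39%.

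**Rejection rate if the plain slope were tested at two-sided 5%** (no drug effect, 306 pairs):

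| Correlation | No shift | 5 ms fall | 8 ms fall |
|---|---|---|---|
| 0 | 5% | 14% | 26% |
| 0.1 | 12% | 20% | 29% |
| 0.3 | 22% | 27% | 37% |
| 0.5 | 32% | 34% | 41% |

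With 250 pairs, correlation 0.1 and no shift gives about 10%. Hence about 10% to 41% for correlation 0.1 to 0.5.

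**With a time factor and random subject intercept** (1000 trials each at correlation 0, 0.3 and 0.5, and shifts of 0, −5 and −8 ms), the slope test rejects in 3.7% to 4.9% of trials, and the mean predicted effect is within 0.2 ms of zero.

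**The case against.** The strongest reply is that the figure is descriptive. SAP 2.4 says "No formal hypotheses will be tested" and SAP 8 says "No formal statistical analysis of the safety data will be conducted". No slope, p-value or interval for QTcF appears in the table or output-listing lists, and Figure 6.3 asks for no band although other figures do. This stands against any claim that the plan inflates a false-positive rate: the rates above apply only if someone tests the line or adds an interval. It does not answer the bias, which is in the line as drawn.

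Second, most of the spread in concentration is between doses. In Protocol Table 2 the 200 mg trough (809 ng/mL) exceeds the 40 mg peak (389). This also stands, and it is why only part of a 5 ms shift leaks through.

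Third, QT safety has other supports: Figures 3.1 and 3.2 show mean QTc change by treatment and time with 95% intervals, there are outlier summaries and individual stopping criteria, and the healthy-volunteer analysis is already done. That limits what rests on this figure but does not correct it.

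A reader might infer that the slope would look non-zero about four times too often. The documents do not support a single multiple: over the assumed range the ratio to nominal runs from about 1 to about 9.

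**Conclusion.** The omission is real and affects the drawn line whether or not it is tested. At planned size an assumed 5 ms post-meal or clock-time shift moves the predicted effect at the 200 mg Cmax by about 1.4 to 2.1 ms, or about 2.0 to 2.7 ms without Part 1 Visit 5. The direction follows the sign of the shift. Pooling four placebo participants at concentration zero does not remove it.

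The mechanism follows from the visit schedule and model; the size rests on assumed inputs. The over-precision point is conditional on a test or interval being reported.

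A reader might also infer that a better model should be read as pass or fail against the 10 ms bound in Protocol 3.2.2. The planned size does not support that. With an SE of about 3 ms and a true effect of 5.38 ms, the upper 90% limit would be about 5.38 + 1.645 × 3 = 10.3 ms. A placebo-adjusted estimate resting on four placebo participants has an SE of about 4.6 to 5.0 ms in simulation.

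**What to change.** In SAP 11.2, replace the plain overlay with a linear mixed model for QTcF change: concentration, nominal visit/time as a factor, and a random subject intercept. Draw that model's line on Figure 6.3. Report the predicted concentration-related change at each dose's geometric mean Cmax with a two-sided 90% CI, labelled descriptive and not read as pass or fail against 10 ms. An active/placebo intercept can be shown as a sensitivity analysis, with its imprecision stated.

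State also whether Part 1 Visit 5 pairs taken on Day 9 or 10 are included, because this changes the size of the bias in a plain line. Reconcile the inclusion of placebo with the PK/PD population named for Figure 6.3, which in SAP 4 requires receipt of GSK3640254.

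The cost is one additional standard model on data already collected. The interval will be wide, but in one set of runs the SD of the estimate fell from about 3.7 ms with the plain line to about 3.0 ms with the mixed model.
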